### 6.1.2 Examination of Subgroups

The following subgroups using LOCF will be examined for the primary efficacy endpoint (i.e., change in hemoglobin from baseline to Day 35):

- Baseline hemoglobin (<10,  $\geq$ 10 g/dL)
- Age (1 to <12,  $\geq$ 12 to 17 years)

The actual value of hemoglobin on baseline, Day 35, and change from baseline to Day 35 will be summarized via descriptive statistics by treatment group and subgroups.

Treatment group difference for change in hemoglobin by subgroup will be assessed with the analysis of covariance (ANCOVA), with treatment and randomization strata (hemoglobin and age categories) as fixed factors and baseline value of hemoglobin as a covariate. Missing value will be imputed using LOCF as specified in [Section 2.3.4](#). Point estimates and associated 95% confidence interval will be reported.

## 6.2 SECONDARY EFFICACY ANALYSES

### 6.2.1 Change in ferritin from baseline to Day 35

The actual value of ferritin on baseline, Day 35, and change from baseline to Day 35 will be summarized via descriptive statistics by treatment group.

Treatment group difference for change in ferritin will be assessed with the analysis of covariance (ANCOVA), with treatment and randomization strata (hemoglobin and age categories) as fixed factors and baseline value of ferritin as a covariate. Missing value will be imputed using LOCF as specified in [Section 2.3.4](#). P-values to test treatment effect will be determined. Point estimates, associated 95% confidence interval and p-values will be reported.

#### Supportive analysis

To assess the robustness of this secondary efficacy analysis, supportive analyses will be performed using the following approach.

#### **MMRM Analysis of Change in ferritin from baseline to Day 35:**

A mixed model repeated measures (MMRM) model will be conducted to provide an analysis under the assumption that data are missing at random (MAR). The MMRM model will include changes in ferritin from baseline to each post-baseline visit as the dependent variables; and treatment group, visit and treatment group by visit interaction as fixed effects; and subjects within treatment group as random effects; and baseline ferritin and randomization strata (hemoglobin and age categories) as covariate. An unstructured covariance matrix will be used to allow for unequal variances between visits. If the model does not converge with unstructured variance – covariance matrix, then the Toeplitz, first-order autoregressive, compound symmetric,

variance components structures will be tried and the covariance structure will be decided based on model convergence status and the AKaike information criterion. The Kenward-Roger approximation will be used to calculate the denominator of degrees of freedom for the fixed effect. If the interaction term is not significant, it will be dropped from the model. No imputation of missing data other than that inherent in the MMRM model will be performed. P-values to test treatment effect on Day 35 will be reported. Point estimates and associated 95% confidence interval will be reported.

### **6.2.2 Change in TSAT from baseline to Day 35**

The actual value of TSAT on baseline, Day 35, and change from baseline to Day 35 will be summarized via descriptive statistics by treatment group.

Treatment group difference for change in TSAT will be assessed with the analysis of covariance (ANCOVA), with treatment and randomization strata (hemoglobin and age categories) as fixed factors and baseline value of TSAT as a covariate. Missing value will be imputed using LOCF as specified in [Section 2.3.4](#). P-values to test treatment effect will be determined. Point estimates, associated 95% confidence interval and p-values will be reported.

To assess the robustness of this secondary efficacy analysis, supportive analyses will be performed using the following approach:

#### **MMRM Analysis of Change in TSAT from baseline to Day 35:**

A mixed model repeated measures (MMRM) model will be conducted to provide an analysis under the assumption that data are missing at random (MAR). The MMRM model will include changes in TSAT from baseline to each post-baseline visit as the dependent variables; and treatment group, visit and treatment group by visit interaction as fixed effects; and subjects within treatment group as random effects; and baseline TSAT and randomization strata (hemoglobin and age categories) as covariate. An unstructured covariance matrix will be used to allow for unequal variances between visits. If the model does not converge with unstructured variance – covariance matrix, then the Toeplitz, first-order autoregressive, compound symmetric, variance components structures will be tried and the covariance structure will be decided based on model convergence status and the AKaike information criterion. The Kenward-Roger approximation will be used to calculate the denominator of degrees of freedom for the fixed effect. If the interaction term is not significant, it will be dropped from the model. No imputation of missing data other than that inherent in the MMRM model will be performed. P-values to test treatment effect on Day 35 will be reported. Point estimates and associated 95% confidence interval will be reported.

### **6.2.3 Change in hemoglobin from baseline to each visit**

The actual value of hemoglobin on baseline, each post-baseline visit, and change from baseline to each post-baseline visit will be summarized via descriptive statistics by treatment group.

#### **6.2.4 Change in ferritin from baseline to each visit**

The actual value of ferritin on baseline, each post-baseline visit, and change from baseline to each post-baseline visit will be summarized via descriptive statistics by treatment group.

#### **6.2.5 Change in TSAT from baseline to each visit**

The actual value of TSAT on baseline, each post-baseline visit, and change from baseline to each post-baseline visit will be summarized via descriptive statistics by treatment group.

#### **6.2.6 Change in Reticulocyte Hemoglobin Content from baseline to each visit**

The actual value of reticulocyte hemoglobin content (CHr) on baseline, each post-baseline visit, and change from baseline to each post-baseline visit will be summarized via descriptive statistics by treatment group.

#### **Supportive analysis**

To assess the robustness of this secondary efficacy analysis, supportive analyses will be performed using the following approach:

#### **MMRM Analysis of Change in CHr from baseline to Day 35:**

A mixed model repeated measures (MMRM) model will be conducted to provide an analysis under the assumption that data are missing at random (MAR). The MMRM model will include changes in CHr from baseline to each post-baseline visit as the dependent variables; and treatment group, visit and treatment group by visit interaction as fixed effects; and subjects within treatment group as random effects; and baseline CHr and randomization strata (hemoglobin and age categories) as covariate. An unstructured covariance matrix will be used to allow for unequal variances between visits. If the model does not converge with unstructured variance – covariance matrix, then the Toeplitz, first-order autoregressive, compound symmetric, variance components structures will be tried and the covariance structure will be decided based on model convergence status and the AKaike information criterion. The Kenward-Roger approximation will be used to calculate the denominator of degrees of freedom for the fixed effect. If the interaction term is not significant, it will be dropped from the model. No imputation of missing data other than that inherent in the MMRM model will be performed. P-values to test treatment effect on Day 35 will be reported. Point estimates, and associated 95% confidence interval will be reported.

### **7. SAFETY ANALYSES**

All safety analyses will be performed on the Safety Population. Safety assessments include:

- Extent of exposure
- Adverse events
- Laboratory assessments (hematology, iron indices, chemistry, and other)

- Vital signs

Baseline of clinical laboratory findings will be defined as the last value obtained before randomization.

## 7.1 EXTENT OF EXPOSURE

For each type of IV administration of FCM, total dose of iron administered (mg), total calculated FCM dose to be given (mg), the number of infusions will be summarized descriptively. For oral iron, the total dose of iron taken (mg), daily dose of iron (mg) will be summarized descriptively.

The study drug exposure will be presented in subject data listings.

## 7.2 ADVERSE EVENTS

Adverse events (AEs) will be coded by System Organ Class (SOC) and Preferred Term (PT) using the Medical Dictionary for Regulatory Activities (MedDRA) dictionary. The verbatim term will be included in the AE listings. Adverse event summaries will exclude preferred terms that describe asymptomatic serum ferritin, TSAT, and reticulocyte values (or changes). This approach is justified by the reporting of these values in efficacy summaries and is consistent with the protocol-defined reporting standards for hemoglobin/hematocrit and low iron indices. For the purposes of this study, non-serious anemia (hemoglobin or hematocrit below the normal range or worsened from baseline) or iron deficiency (iron indices below the normal range or worsened from baseline) will not be considered adverse events. Anemia or iron deficiency will be considered end points if an intervention is required.

A treatment-emergent adverse event (TEAE) is defined as an event with onset date on or after the study drug start date. Partial date TEAE classification rules refer to Section 2.3.4. Only TEAEs will be included in summary tables by treatment group.

The incidence of TEAEs will be summarized as the number (percentage) of subjects with TEAEs within SOC and PT by treatment group. Subjects who report the same PT on multiple occasions will be counted once for the PT: under the highest severity (severe > moderate > mild) CTCAE when summarized by severity and under the closest relationship (probably related > possibly related > unlikely related > none) to study drug when summarized by relationship. If a subject reports multiple PT for a SOC, the subject will be counted only once for that SOC. Events with unknown severity or relationship will be counted as unknown.

TEAEs will be summarized as below.

- An overview table, including number of subjects with
  - TEAEs
  - serious TEAEs
  - study drug related TEAEs
  - study drug related Serious TEAEs

- TEAEs by severity
- TEAEs leading to study drug discontinuation or withdrawal from study
- TEAEs leading to death
- TEAE by SOC
- TEAE by PT
- TEAE by SOC and PT
- TEAE by SOC, PT, and Severity(CTCAE)
- Study drug related TEAEs by SOC, PT
- Serious TEAEs by SOC and PT
- Study drug related serious TEAEs by SOC and PT
- TEAEs leading to study drug discontinuation or withdrawal from study by SOC and PT
- TEAEs leading to death by SOP and PT

Unless otherwise stated, all TEAE tables will be sorted by SOC and PT in decreasing frequency of the number and percentage of subjects in the treatment group.

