### **Study Drug**

#### **Administration**

**Group A (FCM)** will receive 2 doses (Day 0 and Day 7) of FCM at 15 mg/kg to a maximum single dose of 750 mg (whichever is smaller) up to a maximum total dose of 1500 mg. FCM will be administered as either an undiluted IV push at a rate of 100 mg (2 mL)/minute OR in no more than 250 mL of normal saline and infused over 15 minutes.

**Group B (Oral ferrous sulfate)** will receive an age-dependent formulation of oral ferrous sulfate daily for 28 days as follows: participants <12 years of age will receive 6 mg (elemental iron)/kg/day divided into 2 daily doses of an oral liquid formulation, either drops or elixir, and participants  $\geq 12$  will receive 2 daily doses of oral tablets. Infants and children (ages 1 to <4 years) will receive oral ferrous sulfate drops, while children (ages  $\geq 4$  to <12 years) will have the option to receive oral ferrous sulfate elixir or oral ferrous sulfate tablets. Adolescents (ages  $\geq 12$  to 17 years) will receive an oral ferrous sulfate tablet (65 mg of elemental iron/tablet/dose) twice a day (BID). The maximum daily dose for all participants is 130 mg of elemental iron.

**Patient  
Assessments**

All participants who provide informed consent/assent, meet inclusion criteria, and do not meet exclusion criteria will be randomized. Starting on Day 0 (the time of study drug dosing) through Day 35, all randomized participants will be subject to safety assessments including vital signs (including sitting heart rate and blood pressure), laboratory samples include hematology, chemistries and iron indices, and adverse event queries. Participants receiving oral iron treatment will be assessed for degree of compliance.

**Primary  
Endpoint:**

Change in hemoglobin from baseline to Day 35.

**Secondary  
Endpoints:**

Change in ferritin from baseline to Day 35  
Change in TSAT from baseline to Day 35  
Changes from baseline in hemoglobin, ferritin, TSAT, and reticulocyte hemoglobin content throughout the study.  
Pharmacokinetic assessments, including  $C_{max}$ ,  $T_{max}$ ,  $AUC_{0-time\ last}$  measured concentration,  $AUC_{0-infinity}$ ,  $T_{1/2}$ , MRT, Cl,  $V_D$ ,  $V_{Dc}$ ,  $V_{Dss}$ , and  $V_{Darea}$ .

**Study duration  
per participant:**

Approximately 6 weeks

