### **4.4 Withdrawal from Study**

Any participant who wishes to withdraw from the study may do so at any time without the need to justify their decision. The investigator may withdraw a participant from active study treatment at any time if it is felt to be in the best interest of the participant.

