### **4.5 Discontinuation from Study Drug**

Participants may elect to discontinue study drug, but wish to remain in the study for follow-up. In those situations, patients will be asked to continue the normal clinical trial schedule for ascertainment of safety events.

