### 5.2 Drug Administration/Regimen

The Principal Investigator or designee will supervise administration of the study drug to participants. Group B (Ferrous sulfate) the first dose of will be administered before the end of the Day 0 visit.

**Group A:** Group A (FCM) will receive a dose of FCM at 15 mg/kg to a maximum single dose of 750 mg (whichever is smaller) on Days 0 and 7 for a maximum total dose of 1500 mg. FCM will be administered as either an undiluted IV push at a rate of 100 mgs (2 mL)/minute OR in no more than 250 mL of normal saline and infused over 15 minutes.

**Group B:** Group B (Oral Ferrous sulfate) will receive an age-dependent formulation of oral ferrous sulfate daily for 28 days as follows: participants <12 years of age will receive 6 mg (elemental iron)/kg/day divided into 2 daily doses of an oral liquid formulation, either drops or elixir, and participants ≥12 will receive 2 daily doses of oral tablets. Infants and children (ages 1 to <4 years) will receive oral ferrous sulfate drops, while children (ages ≥4 to <12 years)

will have the option to receive oral ferrous sulfate elixir or oral ferrous sulfate tablets. Adolescents (ages  $\geq 12$  to 17 years) will receive an oral ferrous sulfate tablet (65 mg of elemental iron/tablet/dose) twice a day (BID). The maximum daily dose for all participants is 130 mg of elemental iron.

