### **8.5.2 Adverse Events**

Adverse events will be coded by system organ class (SOC) and preferred term (PT) using the Medical Dictionary for Regulatory Activities (MedDRA) dictionary.

The number and percent of participants who report TEAE will be summarized for each treatment group. A TEAE is an event with onset date on or after the study drug start date.

Adverse event summaries will exclude preferred terms that describe asymptomatic serum ferritin, TSAT, and reticulocyte values (or changes). This approach is justified by the reporting of these values in efficacy summaries and is consistent with the protocol-defined reporting standards for hemoglobin/hematocrit and low iron indices. For the purposes of this study, non-serious anemia (hemoglobin or hematocrit below the normal range or worsened from baseline) or iron deficiency (iron indices below the normal range or worsened from baseline) will not be considered adverse events. Anemia or iron deficiency will be considered end points if an intervention is required.

The adverse event profile will be characterized with severity (as graded by the National Cancer Institute Common Terminology Criteria for Adverse Events [NCI-CTCAE]) and relationship (unrelated and related) to study drug. Related adverse events will be events that are possibly or probably related to treatment in the investigator's judgment.

Participants who report the same preferred term on multiple occasions will be counted once for the preferred term: under the highest severity when summarized by severity and under the closest relationship to study drug when summarized by relationship. If a participant reports multiple preferred terms for a SOC, the subject will be counted only once for that SOC.

The number and percent of participants who report treatment-emergent serious adverse events will be similarly summarized for each treatment group. The number and percent of participants who report treatment-emergent adverse events resulting in discontinuation of study drug will be similarly summarized for each treatment group.

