### **7.2.2 Deaths, Serious and Other Significant Adverse Events**

The AEs, serious AEs, AE leading to study discontinuation of study drug or withdrawal from study, and subjects who died during the study will be listed.

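### SAP 7.2 merges adverse events that stop study drug with those that end study participation, so no planned table gives the protocol's drug-stopping count

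*SAP*

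**What the plan says.** - **Protocol 8.5.2** specifies the number and percent of participants by arm: "treatment-emergent adverse events resulting in discontinuation of study drug will be similarly summarized for each treatment group". Leaving the study is not part of that count.
- **SAP 7.2** has one combined category. It appears as a line of the overview table and as a table of its own: "TEAEs leading to study drug discontinuation or withdrawal from study by SOC and PT".
- **SAP 7.2.2** plans the matching listing with the same combination: "AE leading to study discontinuation of study drug or withdrawal from study".
- **Protocol 4.4 and 4.5** treat the two events as distinct. On withdrawal: "Any participant who wishes to withdraw from the study may do so at any time". On stopping drug: "Participants may elect to discontinue study drug, but wish to remain in the study for follow-up".
- **Dosing** differs by arm. The synopsis says that the FCM group "will receive 2 doses (Day 0 and Day 7) of FCM at 15 mg/kg". Protocol 5.2 says that the oral group "will receive an age-dependent formulation of oral ferrous sulfate daily for 28 days". Protocol 7.1 runs adverse event reporting to Day 35 in both arms.
- **SAP Section 9** lists five major changes from the protocol. This one is not among them.

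**The concern.** Two problems meet in one row.

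First, a safety count named in the protocol disappears. A child who stops drug but stays in follow-up and a child who leaves the study are recorded as the same event. The protocol's figure cannot be recovered from the pooled total, because a child may do one, the other or both.

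Second, the row does not mean the same thing in each arm. After a completed Day 7 infusion there is no FCM left to stop, so later FCM entries can only be study withdrawals. An oral-iron entry up to Day 28 can be either event. A reader comparing the two percentages cannot tell how much of a difference is tolerability of the drug, how much is departure from the study, and how much is the length of the dosing period.

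The primary objective covers safety as well as efficacy against oral iron. With about 36 children per arm, one or two children can change the impression that this row gives.

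**Working it through.** **1. Does any other planned output give the protocol's count?**

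- SAP 3.1 (disposition) counts completion and discontinuation of the study, with reasons. It has no line for stopping study drug.
- SAP 7.1 (exposure) summarises the number of FCM infusions and the oral iron taken. A missed second infusion would show, but not whether an adverse event caused it.
- SAP 7.2.2 lists the events under the pooled description.

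No planned table isolates adverse events that stopped drug.

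**2. Opportunity to stop drug, from the schedules**

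- FCM: Day 0 to Day 7, or 7 of 35 follow-up days (7/35 = 20%). After Day 0 only the second dose is left to forgo.
- Oral iron: Day 0 to Day 28, or 28 of 35 days (28/35 = 80%).
- Ratio of windows: 28/7 = 4.

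This ratio already applies to the count in Protocol 8.5.2, before any pooling.

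**3. Illustration of size**

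The documents give no rate of stopping or of withdrawal because of adverse events, so there is no plan figure to reproduce and every rate here is assumed. Let p be the 28-day risk of stopping oral iron (5%, 10%, 20%). Let w be the risk of adverse-event withdrawal from the study by Day 35, equal in both arms (3%, 5%, 10%). Assume that both hazards are constant, independent and the same in each arm.

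- Daily stopping hazard: h = −ln(1 − p)/28.
- Drug stopping alone: oral = p; FCM = 1 − exp(−7h) = 1 − (1 − p)^(1/4).
- Pooled row: oral = 1 − (1 − p)(1 − w); FCM = 1 − (1 − p)^(1/4) × (1 − w).

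Example with p = 10% and w = 5%:

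- Drug stopping alone: FCM = 1 − 0.90^(1/4) = 2.6%; oral = 10%; ratio 3.85.
- Pooled: FCM = 1 − 0.974 × 0.95 = 7.5%; oral = 1 − 0.90 × 0.95 = 14.5%; ratio 1.94.

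| p (oral, 28 days) | FCM, drug stop only | Expected children per 36, FCM v oral | Ratio, drug stop only | Pooled ratio, w = 3% | w = 5% | w = 10% |
|---|---|---|---|---|---|---|
| 5% | 1.3% | 0.46 v 1.8 | 3.92 | 1.85 | 1.57 | 1.30 |
| 10% | 2.6% | 0.94 v 3.6 | 3.85 | 2.30 | 1.94 | 1.54 |
| 20% | 5.4% | 1.95 v 7.2 | 3.69 | 2.71 | 2.36 | 1.88 |

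With no true difference in daily hazard, the drug-stop ratio is about 3.7 to 3.9. Pooling brings it down to about 1.3 to 2.7, depending on w. The pooled row alone would not show which mixture produced it.

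**The case against.** The strongest reply is that this is a table-layout matter. The row is one descriptive line among many in SAP 7.2, with no test or estimate attached. Protocol 7.2 has the action taken recorded for every adverse event. With so few events, a reader could reconstruct most of the picture from the listing, the infusion counts and the reasons for discontinuation. That is largely right, and it keeps the point small. It does not supply the missing table: a count specified in the protocol should not have to be rebuilt from listings.

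A reader might also infer more than the documents support:

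- **That pooling creates a nearly fourfold advantage for FCM.** It does not. That ratio belongs to drug stopping alone, which is the protocol's own count. Under the same assumptions pooling shrinks it.
- **That a lower FCM rate would necessarily be an artefact of the schedule.** It could be, but an equal constant hazard is only an assumption. FCM is two supervised administrations, and oral iron has a dose-reduction step (Protocol 6.3.5) that may take the place of stopping. A real difference in tolerability could move the rates either way.
- **That this is the trial's main tolerability comparison.** Neither document ranks it above all TEAEs, serious, drug-related or severity-graded events, or events of special interest.
- **That no FCM child can stop drug from Day 7 on.** The Day 7 infusion can itself be cut short. The statement holds only once that infusion is complete.
- **That restricting to adverse events with onset by Day 7 makes the arms comparable.** An oral-iron child with onset on Day 6 could stop on Day 12 and still be counted. An FCM child who has completed the second infusion could not.

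**Conclusion.** The point holds as a minor one. Followed as written, the SAP would not produce the by-arm drug-discontinuation count in Protocol 8.5.2, and it does not declare the change. The pooled row mixes two events that the protocol keeps apart, in arms with 7 and 28 days in which drug can be stopped. These findings rest on the text and need no assumption.

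The ratios (about 3.7 to 3.9 for drug stopping, about 1.3 to 2.7 pooled) are illustrations. They depend on assumed rates and on equal, constant, independent hazards, so they should not be read as a forecast of bias. Pooling obscures the imbalance in opportunity but does not cause it. Separating the rows will therefore restore the protocol's count without making the arms equally exposed to the chance of stopping. The primary analysis and its type I error are untouched.

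**What to change.** 1. In SAP 7.2 (overview and SOC/PT table) and 7.2.2 (listing), report separately (a) adverse events that led to stopping study drug, as in Protocol 8.5.2, and (b) adverse events that led to leaving the study. A child who did both appears in both.
2. Footnote the dosing periods: FCM "on Days 0 and 7 for a maximum total dose of 1500 mg", oral iron daily for 28 days.
3. Show (a) by date of drug stop, up to Day 7 and after Day 7, rather than by onset of the adverse event. State the cut in protocol visit days: SAP 2.3.2 numbers the day of first dose as Day 1, so the protocol's Day 7 is study day 8 (7 − 0 + 1). Even up to Day 7 the oral arm has many doses to stop and the FCM arm has one, so the split is for display and does not equalise the arms.
4. If a pooled row is kept as well, list it in SAP Section 9.

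The cost is SAP wording and a few more rows with small counts. Action taken is already recorded for each adverse event (Protocol 7.2). The documents do not say that an exact date of the last oral dose is captured. If it is not, the compliance check at the Day 7 visit should be enough to place a stop before or after that visit. No dose, schedule or clinical rule changes.
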